## 3. Background and Significance

This application proposes a four-year Stage I intervention development project, submitted in response to RFA-AG-18-030. We propose to develop a web-based system that uses distance education methods and provides manuals and protocols to train, certify, and monitor the performance of interventionists to deliver the Savvy Caregiver program (Savvy), an evidence-based dementia family caregiver psychoeducation program. The system will greatly increase the scalability of Savvy. Replacing the need for in-person interventionist training,

it will enable organizations – large or small; community-based or statewide – to offer Savvy to their ever more diverse constituents. Provided to groups of 8-12 (typically) individuals caring for family members living with Alzheimer’s disease or related dementias (PLWD), Savvy employs a well-established mechanism of action based in Social Cognitive theory to promote caregivers’ solution-focused coping behaviors through the acquisition of appropriate knowledge, skills, and outlook and the enhancement of caregiving mastery. The system will provide sponsoring organizations with guidelines and materials for administering Savvy, a program to train and certify staff or volunteer interventionists to lead and locally tailor Savvy, and a process by which to monitor the fidelity of interventionists’ performance. Well-trained Savvy interventionists who faithfully embrace the program’s core principles and its curriculum and are able to adapt program terms, concepts, and even delivery processes to fit the culture and values of caregiver participants are the key to scaling Savvy up to make it widely available to the growing number of dementia family caregivers in the U.S.

The number of PLWD in the U.S. will rise from 5.7 million to 14 million by 2050, and the number of family caregivers who maintain these persons in the community will rise proportionately from 15 million at present. Several psychoeducation programs, including Savvy, have successfully ameliorated the adverse effects of caregiving, but these programs are only minimally available and accessible. Present in 15 states, principally through Administration for Community Living support, Savvy has served more than 15,000 caregivers over the last decade; this represents only one one-thousandth of the U.S. caregiver population. So far, Savvy has been exclusively disseminated through on-site in-person interventionist training by Savvy authors. This costly procedure has limited dissemination to large agencies that have obtained external grant support. The development of this proposed web-based system will take advantage of ubiquitously available distance education methods and platforms to greatly expand access to Savvy for the many organizations, especially small and local organizations that serve the growing number of diverse PLWD and their family caregivers. The activities proposed focus principally on developing and testing the preliminary efficacy of the web-based system. Manuals, slides, handouts, and workbooks will be concurrently developed/revised to harmonize with the system and guide organizations in administering the Savvy program.

#### **4. Goals/Aims**

*Aim 1.* Develop a prototype web-based system for Savvy interventionist training and certification and an accompanying performance fidelity monitoring process. Development efforts will yield web-based components delivered through freely available course management and survey applications (e.g., Canvas; Articulate Rise) that will enable sponsoring entities to train and certify interventionists who can locally tailor Savvy, monitor the fidelity of their performance in delivering Savvy, and assess the program's impact on caregivers.

*Aim 2.* Establish the field-readiness of the system. We will engage three community entities serving culturally, ethnically, and geographically diverse constituencies to collaborate with the study team and expert advisory panel in a highly participatory formative test of the prototype system developed through Aim 1 activities. Results and feedback will inform finalization of materials for the Aim 3 trial.

*Aim 3.* Conduct a field trial of the system. The trial will test the effectiveness of the system and examine its preliminary efficacy in producing expected outcomes (i.e. well-being, mastery) in a diverse group of caregivers participating in programs delivered by newly trained interventionists. Six culturally or organizationally diverse sponsors will recruit 2 individuals each to be trained as Savvy interventionists (12 interventionists) and each sponsor will then recruit at least 20 caregivers to take part in a wait-list, no control group study (N=120) of the performance of the interventionists and the preliminary efficacy of the Savvy program provided by them.

The figure below provides a broad timeline for project activities. While we will begin some Aim 2 activities before all of the Aim 1 activities are complete and some Aim 3 activities before all of the Aim 2 activities are complete, we expect Aim 1 activities to be complete by project month 12 and Aim 2 activities to be complete by the end of the second project year.

		Year 1	Year 2	Year 3	Year 4
Project startup activities	Project startup activities	Start			
	Preliminary Syllabus & Materials	Start	End		
	Storyboard Content & Delivery		Start		
	Materials Production		Start		
Recruit/orient 3 organizations	Recruit/orient 3 organizations				
	Train interventionists		Start		
	Interventionists provide Savvy		Start		
	Evaluate & revise		Start		
Recruit 6 organizations	Recruit 6 organizations				
	Train interventionists			Start	
	Recruit for trial			Start	
	Conduct wait-list trial			Start	
	Analysis & Finalization			Start	

We expect dissemination activities – conference presentations; journal manuscripts – to take place across and beyond the life of the project.

## 5. Study Design

This will be a three-phase project, the goal of which is to establish the readiness of the online learning system for a future Stage III or IV trial that can lead the way to broader use and dissemination of Savvy. In the first project phase, we will develop a prototype web-based system for Savvy interventionist training and

certification and an accompanying performance fidelity monitoring process. This phase will occupy the project's first 14 months and will involve no human subject research participation. Phases 2 and 3 of the study involve human subject research participation. All human subject research activities will be conducted by members of the Emory study team, identified above; no non-Emory study team members will have any contact with Phase 2 and 3 research subjects. The second project phase, which will begin in project month 9 and extend through project month 24, will involve a formative evaluation of the prototype web-based system. In this phase, administrators and interventionists-in-training from 3 collaborating organizations and 36 informal dementia caregivers from these organizations will participate as research subjects. The administrators and interventionists will take part in semi-structured evaluation interviews; the caregivers will be asked to participate in Savvy programs offered by the newly-trained interventionists and they (the caregivers) will be asked to complete pre- and post-Savvy participation interviews both about the effect of the program on them and about their evaluation of the program. Phase 2 results will enable us to revise the interventionist training system, as needed. Once the system is deemed ready, we will, in phase 3, conduct a field test of the system implemented in six culturally and/or organizationally diverse sponsoring agencies. This test will again involve administrators, interventionists-in-training, and 120 dementia caregivers from participating organizations as research participants. The Aim 3 test will principally assess the effectiveness of the system in training interventionists who maintain fidelity to Savvy core principles; this portion of the test involves semi-structured interviews with the administrators, interventionists and a sample of caregivers. The test will also assess the preliminary efficacy of programs led by system-trained interventionists in producing anticipated outcomes in caregiver participants – reduced depression and burden and enhanced caregiving mastery. In this portion of the test, caregivers will be randomly chosen to participate immediately in a Savvy program offered by one of the organization's newly trained interventionists or to participate after a waiting period of 4 months. Those who

take part in the program immediately will be asked to take part in 3 interviews (baseline and then 3 and 6 months after the start of the program. Those in the delayed start group will be asked to take part in 4 interviews (baseline (at the point of signing up for a later program), immediately prior to the beginning of the program and then 3 and 6 months after the start of the program. Standard instruments will be used to assess burden, mood (anxiety and depression), caregiving confidence and mastery, and care recipient well-being.

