### **Setting and location**

The first phase of the study, linked to Aim 1, does not involve human subject research. It only involves the study team, key consultants, and expert advisors who will work at their respective institutions.

The phase 2 and 3 studies are conducted from a single site, the School of Nursing at Emory University. We will centrally and via Zoom videoconferencing software (from Emory) consent the organizational leaders, interventionists trained by the system we developed and dementia family caregivers engaged in Savvy Caregiver programs provided by system-trained interventionists to participation in a wait-list design study in which caregivers from each site will be randomly assigned to immediate participation in a Savvy program offered by one of the newly trained interventionists or to delayed participation in Savvy (after 4 months). Each participant will be asked to complete the same post-program participation survey via Zoom videoconferencing software (from Emory) as in the Phase 2 study, and each will be asked to take part in four phone or video interviews in which Emory staff will administer well-established and validated questionnaires to assess burden, depression, anxiety, and caregiver competence and mastery as well as care recipient well-being. As in the phase 2 study, a sub-sample of caregiver participants (N=18) will be asked to participate in semi-structured interviews – also completed via Zoom videoconferencing software - focused on their perceptions of the interventionist's program leadership skills, any adaptation experiences, and on ways in which they met their own needs and expectations. In both phases (2 and 3) organizational leaders and system-trained

interventionists will be asked to take part in qualitative formative evaluation interviews conducted by Emory study staff.

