addition to sponsor-based debriefings, the semi-structured interviews we will conduct with the interventionists during the Aim 2 and Aim 3 studies will also provide a linkage for them to the overall study and will, hopefully, provide them with a sense of ownership in the developing system.

*Caregivers.* It will only be family caregivers who will be part of the clinical trial component of this study (in Aims 2 and 3). Recruitment into the studies will be through referral from the sponsoring organizations. Each organization will recruit caregivers to take part in Savvy programs provided by interventionists trained in the system we are developing. We will provide organizations with materials they can use to announce Savvy and the studies; we will encourage the organizations to insert these materials into their own standard informational templates (i.e., standard logo and graphics). For caregivers willing to do so, their contact information will be provided to the Emory study team. We will arrange a phone or video call with each during which we will explain the study (Aim 2 or Aim 3 – a caregiver will not be able to take part in both), explain eligibility criteria, and seek informed consent (verbally) for participation. We do not anticipate attrition to be a problem in the Aim 2 study; research contact, following consent, will occur over a very brief period of time. All who consent to the Aim 2 study will take part immediately in a Savvy program and in an on-line survey and (for some) in-person interview conducted by phone or video right after the program. Prolonged retention will be more of a challenge in the Aim 3 study. Those taking part will enter a Savvy program either immediately or after a delay based on scheduling at the individual agencies. For those taking part immediately a series of 3 phone or video interviews will bracket their Savvy participation (at baseline then at 3 and 6 months following baseline. For those with a delayed start, we will conduct 4 interviews (upon sign up, immediately prior to the start of the program and then 3 and 6 months after program completion). To foster engagement with the project, we will prepare and distribute to participants a monthly project newsletter,

featuring tips on exercise and healthy eating and profiles of the study team. We will also send birthday and seasonal holiday cards, as appropriate.

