Results from Savvy participant quantitative fidelity monitoring surveys will be compiled in a simple spread sheet to allow us to see whether there are any notable problems in interventionist performance either within or across sites or in or across interventionists. Likewise, we will be able to compare caregivers' responses about knowledgeability and competence with responses we have received from other caregivers in Savvy programs provided by interventionists who were trained in person by [name] or [name].

Once a cohort of 20 consented caregivers has been formed at any local organization, participants will be assigned (through a random procedure administered by Emory staff) to take part immediately in one of the Savvy programs offered by either of the 2 interventionists or to take part in one of the 2 interventionists' programs after 4 months; follow-up phone or video interviews will be conducted at 2, 4, and 6 months lasting each 1-1.5 hours in length. The audio files from interviews will be saved on Emory School of Nursing's secure share-drive within a password protected folder for 5 years post-study completion.

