### *Participant Discontinuation/Withdrawal from the Study*

Participants are free to withdraw from participation in the study at any time upon request. The reason for participant discontinuation or withdrawal from the study will be recorded on the study REDCap. Subjects who receive all or part of the study intervention will not be replaced.

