## **10. Plans for analysis**

Multi-level mixed effects models (MLM) with random (participant) and fixed (cohort) effects will be employed to test for linear (and non-linear) trajectories of change for the Intervention group versus waitlist

group focusing on the group-by-time effect. To address the primary effect of the Savvy intervention, the Immediate group will be compared to the waitlist delay group, using the first 2 time points (0m-2m) to test for differences between the 2 groups' changes post intervention. Additionally, the combined Savvy intervention effects will be assessed using a paired t-test for the combined immediate group's first 2 time points (0m-2m) with the waitlist delay group's 2 time points before and after beginning Savvy (4m-6m). If there are significant differences between the 2 groups at the time point immediately prior to receipt of the intervention, these "baseline" effects will be included and adjusted for a final analysis of covariance (ANCOVA) model for these change scores. Given that the immediate group will have 3 post-intervention measurements (2m-4m-6m), MLM longitudinal models will also be employed to assess the overall time effects plus planned post hoc comparisons for both the immediate intervention effect and the longer term and sustained effects. Sidak Type-I error rate adjustment (which has higher power than Bonferroni) will be applied for the multiple pairwise time point comparisons. The proposed study design also has the advantage of capturing "baseline" time points for the delay group (0m-2m-4m) which will provide an excellent opportunity to evaluate what if any potential "placebo" effects there may be from being enrolled in this type of study. These initial data captured at 0m-2m-4m for the delay group will also be used to evaluate any potential decline occurring during this time period. All model assumptions will be tested; grand mean centering used to help combat multi-collinearity between variables; and standard diagnostic tests and influence statistics used to test the distributions of the residuals. MLM models utilize all available data for all participants at each time point and have the advantage of adjusting for the missing data over time, where repeated measures ANOVAs do not. Further covariate predictors of missingness (mainly due to attrition) over time will be included to additionally adjust for these confounders SPSS v.24 will be used for all analyses at the 5% significance level.

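### Caregiver interviews are dated from conflicting anchors, and follow-up of delayed caregivers who never start or finish Savvy is left undefined

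*Combined protocol and SAP*

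**What the plan says.** Five places in the combined protocol and SAP bear on when Aim 3 caregivers are interviewed.

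- **5. Study Design.** Immediate arm: "baseline and then 3 and 6 months after the start of the program". Delayed arm: at sign-up, then "immediately prior to the beginning of the program and then 3 and 6 months after the start of the program".
- **Recruitment, Caregivers paragraph.** Immediate arm: "at baseline then at 3 and 6 months following baseline". Delayed arm: at sign-up, then "immediately prior to the start of the program and then 3 and 6 months after program completion".
- **Setting and location.** "each will be asked to take part in four phone or video interviews", with no condition on arm or uptake.
- **Field Methods.** Straight after describing random assignment of both arms: "follow-up phone or video interviews will be conducted at 2, 4, and 6 months". No program trigger is attached.
- **10. Plans for analysis.** The delayed arm has values at 0, 2 and 4 months before Savvy and at 6 months after beginning it. The primary comparison uses 0 and 2 months. A combined before-after analysis uses the delayed arm's 4 and 6 month values.

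Two further sections cover caregivers who leave. Participant Discontinuation/Withdrawal says "The reason for participant discontinuation or withdrawal from the study will be recorded on the study REDCap". Lost to Follow Up starts tracing when a scheduled interview after the intervention is missed. No section states that a caregiver who never starts Savvy is dropped from interviews, and none states that such a caregiver is kept.

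**The concern.** The sections disagree on the event that sets the interview date as well as on the months. 5. Study Design and Recruitment are the only places that itemise the delayed arm's interviews. Both tie everything after sign-up to the program, with no fallback date for someone who does not start or, under Recruitment, does not finish. If no interview falls due, none can be missed, and the tracing procedure is not set off.

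Follow-up in the delayed arm could therefore depend on uptake, which happens after randomization and may be related to outcome: caregivers may decline because they have become too burdened, or because they have improved. Under Recruitment the immediate arm, dated from baseline, would not be filtered in the same way.

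The later delayed-arm values would then describe starters or completers and not everyone assigned. The mixed models use whatever data exist, but they correct for such loss only if observed data explain it, and a non-starter might contribute only the sign-up interview.

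**Working it through.** **Step 1: the stated sample size.** 6 sponsors x 20 caregivers = 120, as in 4. Goals/Aims. The documents give no allocation ratio, uptake rate, SD or effect size. I assume 1:1 allocation, so 60 per arm.

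**Step 2: the schedules side by side**, in months from baseline, with the 4-month wait from 5. Study Design. L is the program length, for which no figure is given. Where the immediate arm is dated from program start, that start is taken to be close to baseline.

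| Section | Immediate arm | Delayed arm | Anchor after baseline |
|---|---|---|---|
| 5. Study Design | 0, 3, 6 | 0, about 4, 7, 10 | program start, both arms |
| Recruitment | 0, 3, 6 | 0, about 4, 4+L+3, 4+L+6 | baseline (immediate); program start and completion (delayed) |
| Field Methods | 0, 2, 4, 6 | 0, 2, 4, 6 | calendar months |
| 10. Plans for analysis | 0, 2, 4, 6 | 0, 2, 4, 6 | calendar months |

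The calendar schedule gives 1 baseline + 3 follow-ups = 4 interviews per person, which agrees with Setting and location. The program-dated schedules give 3 in the immediate arm and 4 in the delayed arm.

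**Step 3: a delayed caregiver who never starts.**
- On the calendar schedule, interviews remain due at 2, 4 and 6 months.
- On the program-dated schedules, if the program means that caregiver's own participation, there is no date for the last two interviews and possibly none for the pre-program one.
- If the program means the scheduled group, the dates still exist.

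**Step 4: which analyses are exposed.** On Section 10's calendar the primary comparison (0-2 months) ends before the delayed arm starts at 4 months, so uptake of the delayed program cannot affect it. The 4-6 month before-after analysis and later follow-up are exposed if interviews are triggered by the program. On the program-dated schedules there is no 2-month interview. The delayed arm's only untreated follow-up is then the pre-program interview, and the randomized comparison would rest on it.

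**Step 5: size, under assumptions.**
- Non-starters: 0.10 x 60 = 6, to 0.20 x 60 = 12.
- Interviews with no due date, if all three after sign-up go: 6 x 3 = 18 to 12 x 3 = 36. Out of 60 x 4 = 240, that is 7.5% to 15%.
- If the pre-program interview survives: 6 x 2 = 12 to 12 x 2 = 24, which is 5% to 10%.
- Shift in the observed delayed-arm mean = non-starter fraction x difference between starters and non-starters. With 0.4 SD: 0.10 x 0.4 = 0.04 to 0.20 x 0.4 = 0.08 SD.
- Wider range: 0.10 x 0.25 = 0.025 to 0.30 x 0.5 = 0.15 SD.

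For scale, the difference detectable with 80% power at two-sided 5% is (1.960 + 0.842) x sqrt(1/60 + 1/60) = 0.51 SD. With 48 left in the delayed arm it is 2.802 x sqrt(1/60 + 1/48) = 0.54 SD.

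**The case against.** A reader might infer that a delayed caregiver who never starts gets no further interview, that the arm's later data come only from those who took up Savvy, and that the immediate arm meanwhile has full data. The documents as a whole do not support this, for four reasons.

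- Field Methods and Section 10 give calendar follow-up, and Setting and location asks everyone for four interviews. On that schedule non-starters still have due dates.
- Savvy is delivered to groups on the agencies' timetables. A group has a start and an end whether or not one member attends, so the program-dated wording need not mean individual participation. On that reading tracing would also apply.
- The contrast between arms rests on Recruitment alone. 5. Study Design dates the immediate arm from program start too.
- The primary comparison in Section 10 precedes the delayed start.

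Non-starters would not necessarily vanish unnoticed either. Data Management compares completers with non-completers, Section 10 adds predictors of missingness, and the monitoring reports cover retention and data completeness.

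All of this stands, and it limits the point. It does not remove it. The calendar sections conflict with the itemised schedules, nothing says which prevails, and no sentence commits the study to interviewing caregivers regardless of uptake. The months could be harmonised and the program trigger left in place.

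**Conclusion.** The supportable finding is a conflict of anchors (program start, program completion, baseline, calendar months) together with unspecified follow-up of delayed caregivers who do not start or finish. It should be corrected. Selection of the delayed arm's later data by uptake is a conditional risk: it arises if 5. Study Design or Recruitment is followed and the program is read as the caregiver's own participation.

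The likely size is modest, 0.04-0.08 SD in the delayed-arm mean, against a detectable difference of about 0.51 SD. The uptake rate, the 0.4 SD difference and the 60 per arm are all assumptions. Non-completers under Recruitment would add to it. Confidence is medium, because the documents do not show which schedule will be run.

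**What to change.** Reconcile 5. Study Design, Setting and location, Recruitment, Field Methods and Section 10 to one schedule, timed from random assignment and using the same months in both arms, as Field Methods and Section 10 already imply. Then:

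- state that each interview takes place whether or not Savvy has been started, stopped or finished;
- hold the delayed arm's end-of-wait interview at its fixed month even if the program is postponed or declined;
- record actual start date and sessions attended as data, not as triggers.

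The work is protocol wording and REDCap scheduling from the assignment date. There are three costs.

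- When a program slips, some interviews will fall a few weeks off its dates.
- The immediate arm has one interview more than 5. Study Design and Recruitment list. With 60 caregivers and the $25 honorarium, that is 60 x 25 = $1,500 plus staff time. It is no more than Setting and location and Field Methods already plan.
- A calendar ending at 6 months stops about 6 - 4 = 2 months after the delayed start. If the sponsor wants the longer follow-up of that arm, it should be added at fixed months from assignment.
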